### **WP1 - Analyses**

Length of lie is of interest as both an outcome (under what circumstances is a long lie more likely) and as a predictor of health outcomes and future resource use.

WP1.1 We will provide a descriptive analysis of length of lie, stratified by patient demographics and the characteristics of calls and resulting attendances, including features which have implications for the care trajectory of the patient (e.g. time of day of the call/attendance, seasonality) to examine seasonal pressures. We will explore the relationship between length of lie and key outcome variables using descriptive and visualisation methods.

WP1.2 We will examine the impact of the length of lie on key outcomes via a series of regression models. Key outcomes will include ambulance conveyance (vs see and treat); number of investigations at ED; acute admission to hospital; number of treatments received; discharge to care home or 'step down' or intermediate care; 12-month mortality; number of and time to first readmission within 12 months; number of and time to first unplanned ED attendance within 12 months; number of and time to first NHS 111 call within 12 months. These will consist of logistic, Poisson, and other regression models as appropriate. Key outcomes will be discussed with both the project management group and the PPI group to ensure all potential relevant outcomes have been included.

These analyses will include length of lie as a continuous variable, as a dichotomous variable based on the NICE 1-hour definition of a long lie in logistic regression, and dichotomised based on other possible explanatory thresholds identified in WP1.1. This will quantify the impact of a long lie on patient health outcomes, and indicate whether 1 hour is the most appropriate threshold to consider a long lie in terms of health outcomes.

These analyses will be carried out as adjusted and unadjusted analyses, including appropriate demographic covariates such as age, sex, ethnicity, deprivation indices, care home residence, indications of frailty and/or comorbidities, time of day, season and any key clinical observations recorded by ambulance crew.

Analysis will provide an estimate of association between length of time lying after a fall and outcomes. However, the assessment of clinical risk undertaken initially will partly determine the length of time left lying after a fall (i.e. ambulance response times may be shorter where a patient has additional risk factors). This means that a confound in terms of fall severity/clinical risk is possible. Since the data is not currently available to assess what analyses may be possible, we planned a cautious associative analysis in the first instance. This will remain the primary analysis; an assessment of clinical risk will be included as a covariate in the analyses where available.

The possibility of additional causal inference methods will be assessed on receipt of the data and if feasible will be undertaken as a supplementary analysis. This may involve the use of matching (although if systematic differences in

clinical severity exist between groups this may reduce sample size dramatically). Alternatively approaches such as the use of instrumental variables may be used (e.g., distance of event from nearest ED may be an appropriate instrument).

WP1.3 Will explore the impact of environmental, geographical and seasonal variables on the length of lie. This will be undertaken with length of lie as a continuous variable in linear regression and as a dichotomised variable based on results from WP1.2. This will provide an indication of the factors driving the likelihood of a long lie. Results from this analysis in context with those from WP1.2 will facilitate an understanding of targets for future intervention in order to address key outcomes.

PPI will discuss definitions of a long lie at the start of the WP to enable their views to feed into the analysis and the variables used, as there may be PPI perspectives that are relevant that have not been documented in the literature. Their views on the parameters of what is a long lie and how this may vary in different contexts e.g. a fall in the home vs a fall outside. This may help inform any scenario analysis. Results will then be fed back to PPI, their views on the findings discussed and different definitions validated. Proposed definitions will then be fed into the workshops (WP7).

Early analyses from WP1 will be used to feed into WPs 3-6.

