#### **4.1 Objectives**

- To characterise the frequency and duration of long lies in ambulance patients using data from one UK region held within the CUREd+ routine linked dataset;
- To understand the care trajectory, health outcomes, and health resource use of patients after a long lie using the CUREd+ linked dataset;
- To understand the mechanisms by which a long lie impacts care trajectories using hospital notes review for a subset of 200 patients identified from ambulance service data;

- To identify interventions used to mitigate the impact of long lies before arrival at hospital using a survey of ambulance services and social care providers;
- To understand how key stakeholders mitigate long lies using staff interviews;
- To understand the impact of long lies on patient and carers using interviews with patient and carers;
- To refine the definition of a long lie that is likely to cause harm and identify actions to reduce their consequences for patients

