### **WP3: Understanding the mechanisms for impact of long lie using patient notes review**

WP1 will provide an overview of the patient journey for a cohort of patients who have had called 999 after a fall. Within WP3 a more detailed and nuanced description of the patient journey will be described by undertaking detailed notes review to understand the post-fall management and treatment pathway, and the aspects of their care that could be attributed to the long lie rather than the injuries resulting directly from the fall.

A detailed hospital notes review for a subset of 200 patients (50 patients at each of the four hospitals with an Emergency Department within the Yorkshire and Humber region) to understand which complications from the long lie lead to changes in patient care trajectory will be undertaken (i.e the mechanisms for impact of long lie). Ambulance records will be used to identify a sample of 50 patients who had a long lie (as defined by CUREd+ WP1 analysis) who were transported to each of four participating hospitals within the YAS area. We will invite expressions of interest from all eligible hospitals (i.e those with an Emergency Department) within the Yorkshire and Humber region and select hospitals with the highest incidence of long lie, ensuring a wide geographical spread. We will sample consecutively until we have a mixture of short and long lies (as defined by WP1).

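### WP1.2 judges the 1-hour threshold by comparing dichotomies, which cannot tell a real threshold from an artefact of selection

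*Protocol*

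**What the plan says.** The protocol's WP1 - Analyses section sets out a sequence.

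- **WP1.1** describes the distribution of lie length and also looks at outcomes: "We will explore the relationship between length of lie and key outcome variables using descriptive and visualisation methods".
- **WP1.2** models the outcomes in three ways. First: "These analyses will include length of lie as a continuous variable". Second: "as a dichotomous variable based on the NICE 1-hour definition of a long lie in logistic regression". Third: "dichotomised based on other possible explanatory thresholds identified in WP1.1". The stated result is that this will "indicate whether 1 hour is the most appropriate threshold to consider a long lie in terms of health outcomes". The WP1 - Data collection section draws the same conclusion from regressions under different definitions of a long lie, without mentioning a continuous term at that point.
- **WP1.3** models lie length as a continuous outcome and "as a dichotomised variable based on results from WP1.2".

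The result travels further. The WP2 cost models use lie length dichotomised as in WP1, WP3 identifies long lies by the WP1 definition, and proposed definitions go to the WP7 workshops. The objective served is "To refine the definition of a long lie that is likely to cause harm" (section 4.1). The only validation of definitions that is mentioned is discussion with the PPI group. A full SAP is promised and is not at hand.

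**The concern.** Two problems are joined here. Cut-offs suggested by looking at outcomes, and then tested on the same outcomes in the same records, reach significance too easily. More fundamentally, a significant dichotomy does not show that a threshold exists. If risk rises steadily with time on the floor, people above almost any cut-off do worse than people below it, so many cut-offs will be significant and one will fit best. Where that one falls depends on the shape of the curve and the spread of lie times, not on any point at which harm begins.

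The protocol intends the refined definition to inform call triage and dispatch (sections 1.4 and 8). A cut-off that merely reflects the distribution of lie times could be taken for a clinical boundary and passed through four later pieces of work.

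**Working it through.** **The plan's own figure.** About 16,000 documented long lies are expected among at least 115,000 cases (WP1 - Data collection). Section 1.1 gives 39% on the floor, of whom 35% had a long lie: 115,000 × 0.39 = 44,850, and 44,850 × 0.35 = 15,698, which is within 2% of 16,000. The figure reproduces only if the 115,000 are all fall calls. The protocol labels them as patients unable to get up, and 35% of 115,000 would be 40,250. The simulations use N = 44,850. Under no association the false-positive rate depends on the share of patients either side of each cut-off, not on N.

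**Assumptions not in the protocol.** Lognormal lie times with 35% over 60 minutes and log-SD 0.8, 1.0 or 1.4; one binary outcome at about 20%, with logit risk = log(0.25) + f(t); ten candidate cut-offs from 30 to 720 minutes. Each cut-off is tested two-sided at 5% by z = (p_above − p_below) / √[P(1 − P)(1/n_below + 1/n_above)], where P is the overall risk. The best cut-off is the one with the largest |z|.

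| Assumed truth | Log-SD | At least one cut-off significant | 1-hour split significant | Where the best cut-off falls |
|---|---|---|---|---|
| No association | 0.8-1.4 | 26-32% | 5% (nominal) | spread over 30-720 min |
| OR 1.10 per doubling | 0.8 / 1.0 / 1.4 | 100% | 100% | 30-60 min in 88% / 90% / 86% |
| OR 1.10 per hour | 0.8 / 1.0 | 100% | 100% | 90-240 min in 86% / 79% |
| OR 1.10 per hour | 1.4 | 100% | 100% | 360-720 min in 98% |
| OR 1.05 per hour | 0.8 / 1.0 / 1.4 | 99% / 100% / 100% | 80% / 98% / 100% | 60-240 min in 76% / 120-360 min in 77% / 360-720 min in 89% |
| Step, OR 1.2 at 60 min | 0.8-1.4 | 100% | 100% | 60 min in 97-99% |
| Step, OR 1.2 at 120 min | 0.8-1.4 | 100% | 65-99% | 120 min in 93-95% |

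A second set of simulations used log-SD 0.9 and 1.3, an event rate of about 17%, ten cut-offs from 30 to 480 minutes, best cut-off by likelihood, and 400 runs per distribution. It agreed: 24-29% of runs had a significant cut-off under no association. With OR 1.10 per doubling, every cut-off up to 180 minutes was significant in all runs.

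**What would separate the cases** (N = 44,850, log-SD 1.0):

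- Choosing the cut-off in one half and testing it in the other lowers the false-positive rate under no association from 31.7% to 5.0% (2,000 runs).
- That split does not show that a threshold exists. With smooth risk the chosen cut-off was still significant in 100% of held-out halves (60 runs for each curve).
- Comparing the best step (counted as 3 parameters) with a 4-knot restricted cubic spline in log time (4 parameters) by AIC does separate them. The spline won in 100% of runs when the truth was smooth and in 7% when it was a step at 60 minutes (60 runs each).

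**The case against.** The strongest reply is that the plan is broader and more tentative than its threshold clause suggests. Four points carry weight.

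- A reader might infer that only dichotomies are planned. The text does not support that: WP1.2 also models lie length continuously, and WP1.3 has it as a continuous outcome. But no functional form is given for the WP1.2 term, a single linear term could not test for a threshold, and the statement about 1 hour is not tied to it.
- A reader might infer that the plan could never show that 1 hour is right. That is too strong, since a true 60-minute step was picked in 97-99% of runs. The difficulty is that the output looks the same when there is no step.
- A reader might infer that the protocol fixes a rule of taking the best-fitting cut-off from outcome plots. It states no such rule. WP1.1 also describes lie length itself, and PPI views on definitions feed in at the start. Choosing the best of ten is an assumption of the simulation. That outcome exploration suggests some of the cut-offs is the natural reading, though not an explicit one.
- Candidate lists, knots and hold-out samples belong in the SAP, and their absence from the protocol is not the complaint. The protocol itself says where the alternative cut-offs come from, models them in the same cohort, and states what will be concluded.

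It is also fair that significance under a smooth dose-response reflects a true association and is not a false positive. That is why significance cannot be read as evidence of a threshold. PPI and workshop discussion mean the cut-off is not adopted automatically, but discussion cannot correct statistical selection.

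**Conclusion.** The point holds in this limited form: the comparison of dichotomies cannot distinguish a real threshold from a product of selection, so it does not support the conclusion that the protocol attaches to it. The location of the best cut-off under smooth risk moved from 30-60 minutes to 360-720 minutes according only to the assumed curve and the spread of lie times.

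The percentages rest on assumed lie-time distributions, event rates, effect sizes and ten candidates, and show direction and rough size only. Inflation of odds ratios was not quantified and is not claimed. Because the definition of a harmful lie is a stated objective and success criterion, this should be changed before a cut-off passes to later work packages.

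**What to change.** - Base the threshold question on the continuous analysis already planned in WP1.2, fitted flexibly, for example with a restricted cubic spline in log-minutes. Report adjusted absolute risks with confidence intervals at fixed times that include 1 hour.
- Compare step with smooth models before claiming any threshold, and tie the statement about 1 hour to that comparison.
- If a cut-off is still derived, either fix the candidates in advance, or select and estimate it in separate random halves split by patient, or use cross-validation or the bootstrap. Report the uncertainty in its location. The halves should not be calendar periods: the WP1 - Data collection section accepts that Covid-19 may alter the balance of long and short lies, so a calendar split would mix validation with period change. A hold-out sample alone is not enough, because it does not show that a threshold exists.
- In WP1.3 keep the continuous outcome and use the fixed 1-hour split, with any derived cut-off labelled exploratory.

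The cost is more analysis work and no new data. If the sample is split, a derived cut-off is estimated less precisely, on about 44,850 / 2 ≈ 22,400 cases in each half.

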## **WP2 Understand the resource use of ambulance service patients after their fall**

### **WP2 - Data collection**

Urgent and Emergency Care service access events in the 12 months following an ambulance call after a fall will be assigned a unit cost based on Healthcare Resource Group (HRG) reference costs. These events include ambulance journeys, ED attendances, acute, non-elective inpatient admissions and subsequent hospital stays and outpatient events (where available). Where possible, this will be calculated using the NHS National Schedule of Costs (NHS England 2021/22 cost data) for the appropriate year. In the event that HRG codes are unavailable in CUREd+, estimated costs will be calculated based on average costs by specialty, attendance type, or ambulance service level. Where costs for that year may not be available, costs for the most recent available year will be used and adjusted using the NHS Cost Inflation Index (Jones 2023). Costs will be aggregated on a monthly basis to produce a total cost per patient per month for the 12 months following a fall.

In the event additional fall events occur within the 12-month fall follow-up period for a given patient, the additional fall will be considered a new 'index' event. The initial 12-month follow-up period related to the first fall will be censored and costs subsequent to the second fall will be modelled as occurring in the new 12-month follow-up. This will be adjusted for in the regression models. This is likely to result in wider confidence intervals for later months in the follow-up period. Confidence intervals will also be impacted for the loss of patients to follow-up, through either missing data, migration, or death during the follow-up period.

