#### **1.4 Plain English Summary**

When a person is unable to get up off the floor for a prolonged period of time after a fall, this is referred to as a 'long lie'. Around 1 in 3 adults over 65 have at least one fall a year and around one in 5 of these will be a long lie (over 1 hour). People who have a long lie may suffer a number of complications, including dehydration, pressure injuries, muscle and tissue damage and psychological harm. Longer ambulance response times due to growing pressure on ambulance services means that people are being left on the floor for increasing periods of time. The problem of long lies may therefore be leading to worse health outcomes for an increasing number of people. Whilst there has been a lot of research to understand how to prevent people falling, there is currently little information about how to manage people once they have fallen. Existing advice given to patients who have fallen assumes that an ambulance will arrive quickly. It is also based around concerns that the patient may have a hip fracture and need surgery. However, most people who fall do not have a fractured hip, and current advice that people should not be moved or should restrict fluids may be more dangerous for people who have a long lie.

We wish to understand more about what happens when people have a long lie and how people can be helped whilst waiting for an ambulance. We will work with patients and the public as well as relevant health and social care organisations. We will do this using 7 different research activities:

1. We will analyse an anonymised dataset of linked ambulance, emergency department and hospital patient records to understand which patients have a long lie and what happens to them after they have fallen. We will look at what health and social care services patients used during the 12 months after their fall and whether this is different for people who had a long lie. We will also use this data to understand the length of lie where the risk of long-term damage is increased. This will help ambulance services when deciding how to prioritise calls in future.
2. We will apply standard NHS and social care costs to the linked dataset to estimate the cost of care for people following their fall. We will compare costs of people who have a short lie with those who have a longer lie.

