#### **4.2 Outcomes**

- Describe the frequency and duration of lies in ambulance patients and refine the definition of a harmful lie.
- Understand the care trajectory of patients who have fallen with and without a long lie, their health resource use and care outcomes within 12 months of their fall and long lie.
- Improve understanding of morbidity associated with the injury resulting from the fall, and that relating to the long lie.
- Understand how key stakeholders currently manage and mitigate for long lies and where there is variation in practice/understanding that may be harmful
- Understand the patient and carer perspective of long lies, the psychological impact and areas where advice about how to manage a long lie are required

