### **WP2 - Analysis**

Aggregated, monthly cost data per patient will be modelled using two-part 'hurdle' Gamma regression models, with length of lie as a primary independent variable. Models will explore the influence of length of lie as a continuous and dichotomised variable as described in WP1. The use of monthly cost data as the primary outcome supports estimates of costs associated with length of lie for each month following the index fall event, facilitating an understanding of whether cost differences increase, decrease, or remain stable over the 12 month follow-up period.

A series of models will be developed to explore the influence of length of lie on resource use. Unadjusted models with only length of lie and month number as predictor variables will give a crude estimate of the influence of length of lie. Patient ID will be included as a random effect to account for individual level clustering.

Second, covariate-only models will establish a 'baseline' against which to assess the adjusted influence of length of lie on cost outcomes. These will include demographic data including age, sex, deprivation decile and ethnicity; clinical characteristics including comorbidities; and features of the incidence including time of year, time of day and distance to nearest ED. The precise list of covariates will depend on data quality and learning from WP1.

Finally, fully adjusted models will include length of lie as a main predictor in conjunction with covariates listed above. This will give adjusted estimates of the effect of length of lie. Likelihood ratio tests will compare the adjusted models with the baseline models to determine the impact of including length of lie as a predictor over and above the covariates. The above models will be developed for all healthcare related costs, and separately for costs related to ED attendances, acute admissions, ambulance calls, NHS 111 calls and outpatient costs.

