The primary analysis will consider 'Month 1' to be the calendar month in which the index fall occurs. This will therefore consider month 1 to be the same for falls occurring on the first or last day of the month. This may result in issues around the accuracy of predictions of monthly costs (although distribution is expected to be the same for long and short length of lie). Sensitivity analysis will examine a different date alignment, whereby 'Month 1' will be considered the same calendar month for a fall occurring in the first half of a month, and the subsequent calendar month for a fall occurring in the second half of a month.

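### The follow-up clock for NHS 111 and ambulance-call outcomes starts before the lie has ended, so contacts made from the floor can be counted as effects of the lie

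*Protocol*

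**What the plan says.** **Exposure.** Protocol section 5, WP1 - Data collection, starts the lie at the recorded time of injury or illness. Where that is missing, the interval from call or incident time to crew arrival at scene may be used. Crew arrival is the only end point named.

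**Outcome and cost window.** WP2 - Data collection gives two origins in one paragraph. One is the ambulance call: "Urgent and Emergency Care service access events in the 12 months following an ambulance call after a fall will be assigned a unit cost". The other is the fall, since monthly costs are summed "to produce a total cost per patient per month for the 12 months following a fall". WP2 - Analysis sets Month 1 as the calendar month of the index fall. Section 1.4 also counts service use from the fall. Section 4.2 refers to "their health resource use and care outcomes within 12 months of their fall and long lie", which does not name the end of the lie as the start.

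**Outcomes concerned.** WP1.2 includes "number of and time to first NHS 111 call within 12 months", with no lower time limit. WP2 - Analysis plans separate cost models that include "ambulance calls, NHS 111 calls and outpatient costs".

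No section starts the window at crew arrival, or sets aside contacts made between the fall and crew arrival.

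**The concern.** A patient who waits longer on the floor has more time, and more reason, to ring for help again. If those calls fall inside the follow-up window, part of the outcome is produced during the exposure and tends to increase with it. The 111 results could then rise with length of lie even if patients fared identically once off the floor.

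This is a fault in the time origin, not confounding. Covariate adjustment and matching do not remove events that happened during exposure. An instrument that shifts time on the floor shifts calls made from the floor as well. The WP2 sensitivity analysis realigns calendar months and does not separate contacts before crew arrival from those after it.

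The direction matches the starting theory in section 3 that longer lies do more harm. WP1.2 will use its models to quantify the impact of a long lie and to judge whether 1 hour is the right threshold. Section 8 intends the findings to inform call triage and dispatch priority.

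**Working it through.** **1. Order of events.** Fall, then ambulance call, then crew arrival. The lie ends at the third. The two WP2 origins are the second and the first. Both precede the end of exposure.

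- With the call as origin, the overlap is the call-to-arrival wait.
- With the fall as origin, the overlap is the whole lie.
- A 111 call made after the fall but before the index 999 call counts under the second origin and not the first, so the two origins give different data.

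**2. Length of the overlap.** Section 1.1 gives mean response times of 107 minutes (category 3) and 139 minutes (category 4). As a share of 12 months (8,760 hours):

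- 107/60/8,760 = 0.020%
- 139/60/8,760 = 0.026%

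The overlap is negligible as person-time. It matters only if calls are concentrated in it.

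**3. Illustration with no true effect.** The protocol has no figure of its own to reproduce. The following are assumptions:

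- λ, the call rate after the lie, is the same in both groups: 0.5, 1 or 2 per year.
- ρ, the call rate while on the floor after the index call: 0.01, 0.05, 0.1 or 0.2 per hour.
- Time on the floor after the call: 0.5 h for a short lie; 1.78 h or 2.32 h for a long lie (107 and 139 minutes).

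Rate ratio = (λ + ρ·h_long)/(λ + ρ·h_short). Each cell gives 1.78 h / 2.32 h.

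| λ | ρ = 0.01 | ρ = 0.05 | ρ = 0.1 | ρ = 0.2 |
|---|---|---|---|---|
| 0.5 | 1.025 / 1.036 | 1.122 / 1.173 | 1.233 / 1.330 | 1.428 / 1.606 |
| 1 | 1.013 / 1.018 | 1.063 / 1.089 | 1.122 / 1.173 | 1.233 / 1.330 |
| 2 | 1.006 / 1.009 | 1.032 / 1.045 | 1.063 / 1.089 | 1.122 / 1.173 |

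Example: λ = 1, ρ = 0.05, h_long = 1.78 gives (1 + 0.0892)/(1 + 0.025) = 1.063.

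**4. Time to first call.** Chance of any call on day 1 = 1 − exp{−[ρh + λ(24 − h)/8,760]}. In the same example this is 0.0876 after a long lie and 0.0273 after a short one, a ratio of 3.21. Across the grid the ratio is 2.2 to 4.25, with no true difference after the lie.

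**5. Would the analysis pick it up?** WP1 expects at least 115,000 cases and about 16,000 long lies, leaving 99,000 others. With SE(log RR) = √[1/(16,000·m_long) + 1/(99,000·m_short)], where m is the mean calls per patient, a two-sided 5% Poisson test without overdispersion gives a false positive with probability 0.19 to 0.85 at ρ = 0.01. From ρ = 0.05 upward the probability is about 1.00.

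**6. After the change.** If the window opens at crew arrival in both groups, the same illustration gives λ/λ = 1.00, by construction.

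**The case against.** The strongest reply is that the protocol nowhere says contacts made from the floor will be counted, and that it defers detail to an SAP, which could exclude them. Other wording suggests that use after the lie is meant: the objectives speak of resource use after a long lie, WP1 - Analyses of future resource use, and WP1 - Data collection of subsequent ambulance re-contact. This shows intent but does not settle the matter. The word subsequent has no reference point there and does not cover 111 calls. Nor is the protocol merely silent: it states origins, and an SAP that followed them would inherit the overlap.

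Several limits do stand:

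- Repeat 999 calls are weaker ground. They are not in the WP1.2 outcome list, and the events costed under WP2 - Data collection are ambulance journeys. A second call while waiting does not itself create a second journey.
- NHS 111 calls are absent from that list of costed events too, although WP2 - Analysis gives them a cost model.
- With the call as origin, time on the floor before the call lengthens the lie but not the overlap, so the link between the two is only partial.
- Calls prompted by a long wait are real resource use. Whether they belong in a cost total depends on the perspective taken.
- Some patients may be up before the crew arrives, so crew arrival is an imperfect end of lie.

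A reader might infer that all 12-month outcomes, or the total Month 1 cost difference, are inflated. The documents do not support that. The mechanism needs contacts made during the wait, and no calculation shows a material effect on admissions, investigations or total cost.

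**Conclusion.** The point holds for the NHS 111 count, the time to first 111 call and the 111 cost model. It extends to the ambulance-call cost model only if repeat calls are costed. For these, the stated origins precede the end of exposure as the protocol measures it. Followed as written, they can produce an association with length of lie when there is no later effect.

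The size is not known. The range of about 1.01 to 1.6 rests wholly on assumed call rates and waiting times, and at its low end the bias is negligible. Time to first 111 call is the most exposed, because contacts made from the floor become first events within hours. The false-positive probabilities also assume no overdispersion and are illustrative only. The associative framing of the primary analysis does not remove the problem, which lies in what is counted as an outcome.

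**What to change.** Use one origin in WP1 - Analyses and WP2 - Data collection for the 111 and ambulance-contact outcomes and their cost models: the end of the lie as the protocol measures it, crew arrival at scene. Assign every 111 and 999 contact between the fall and crew arrival to the index incident. Report those contacts separately as a feature of the wait, so that their number and cost stay visible. Align the service-use wording in sections 1.4 and 4.2 and the Month 1 definition with this, and say whether repeat ambulance calls are costed.

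The cost is a sentence or two, a timestamp filter on a field that WP1 already names, and slightly fewer counted contacts.
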